## 2.3. Study Endpoints

### 2.3.1. Safety Endpoints

The safety endpoints of this study include the following:

- Nature, frequency, and severity of adverse events, including serious adverse events, adverse events leading to discontinuation and possible corticosteroid-related adverse effects
- Change from baseline in vital signs and clinical laboratory test results (including complete blood count and blood chemistry)

### 2.3.2. Efficacy Endpoints

For efficacy endpoints, Baseline is defined as stated in Section 6.1.1. Unless specified otherwise, endpoint comparisons will be based on differences between randomized treatment groups. Week 37 visit, is the planned last assessment within the Blinded Treatment Period (as

defined in Section 3.1) over which the primary and key secondary efficacy endpoints will be evaluated. Additional endpoints may be evaluated through the Week 61 visit, or the planned last assessment within the Open-Label Extension Period, which begins after administration of the first dose of open-label PRN1008.

### **2.3.2.1. Primary Efficacy Endpoint**

The primary efficacy endpoint of this study is the proportion of patients who are in CR from Week 29 to Week 37 with a CS dose of  $\leq 10$  mg/day.

### **2.3.2.2. Key Secondary Efficacy Endpoints**

The key secondary efficacy endpoints of this study include the following, ranked in order of importance:

1. Cumulative CS dose from Baseline to Week 37
2. Cumulative duration of CR with a CS dose  $\leq 10$  mg/day, from Baseline to Week 37
3. Time to first CR with a CS dose  $\leq 10$  mg/day CS, from Baseline to Week 37

### **2.3.2.3. Other Secondary Endpoint(s)**

The other secondary efficacy endpoints of this study include the following:

- The proportion of patients who are in CR from Week 29 to Week 37 with a CS dose of  $\leq 5$  mg/day
- The proportion of patients who have a PDAI score  $< 3$  from Week 29 to Week 37 with a CS dose  $\leq 10$  mg/day
- Cumulative duration of CR with a CS dose  $\leq 10$  mg/day from Baseline to Week 61, and from baseline to Week 109
- Cumulative duration of CR with a CS dose = 0 mg/day from Baseline to Week 61, and from baseline to Week 109
- Glucocorticoid Toxicity Index (GTI) score at Week 37
- Change in PDAI score from baseline to Weeks 5, 13, 25, 37, 61 and 109
- Change in Autoimmune Bullous Disease Quality of Life (ABQOL) score from baseline to Weeks 5, 13, 25, 37, 61, and 109
- Proportion of patients with ABQOL Score of zero at Weeks 5, 13, 25, 37, 61, and 109
- Change in EuroQOL-5 Dimension 5 Level (EQ-5D-5L) results (visual analog scale [VAS] results and individual dimension) scores from Baseline to Weeks 5, 13, 25, 37, 61, and 109
- Time to first CR with a CS dose  $\leq 10$ mg/day from Baseline to Week 61, and from Baseline to Week 109
- Total number of disease flares/relapses from initial CDA to Week 37
- Time to initial flare/relapse from initial CDA to Week 37
- Proportion of patients with 3 or more lesions within 1 month that do not heal spontaneously within 1 week, or by the extension of established lesions, from Baseline to Week 37.
- Proportion of patients with at least one disease flare/relapse from initial control of disease activity (CDA) to Week 37.

- Cumulative duration of CR with a CS dose  $\leq$  10 mg/day, from Week 37 to Week 61.
- Cumulative duration of CR with a CS dose = 0 mg/day, from Week 37 to Week 61

### 2.3.3. Pharmacokinetic/Pharmacodynamic Endpoints

The pharmacokinetic (PK) endpoints of the study include plasma concentrations of PRN1008 as follows:

- Plasma concentrations of PRN1008 at approximately the time of maximum concentration at Day 1 and at varied subsequent time points.

The pharmacodynamic (PD) endpoints of the study include

- the change from baseline in anti-dsg1 and anti-dsg3 autoantibody levels by enzyme-linked immunosorbent assay (ELISA) at Weeks 13, 25, 37, 49, 61, and 109.

The calculation of parameters for population PK analysis will be described and reported separately.

### 2.3.4. Exploratory Endpoints

Exploratory endpoints and analyses include the following:

- Exploratory PK/PD analysis will examine the effects, if any, of covariates on PK and/or PD, and the relationship between PK, PD and efficacy in this population
- Number and type of hospitalizations, outpatient medical visits, concomitant medication use, adverse events and other relevant outcomes
- Change from baseline in PDAI by visit and the temporal relationship to changes in quality of life and health economic variables
- Proportion of patients with relapse after achievement of CR between Baseline and Week 61, and between Baseline and Week 109
- Proportion of patients initially randomized to PRN1008 that are in CR with a zero CS dose, from Week 53 to Week 61 (no randomized treatment comparison)
- Proportion of patients initially randomized to placebo that are in CR with a zero CS dose, from Week 53 to Week 61 (no randomized treatment comparison)
- Change in Treatment of Autoimmune Bullous Disease Quality of Life (TABQOL) score from Baseline to Weeks 5, 13, 25, 37, 61, and 109
- Total number of disease flares/relapses from Week 37 to Week 61, and from Week 61 to Week 109
- (Optional) Blood samples for exploratory analysis of vaccine IgG response during treatment.

### 2.3.5. Long Term Extension Endpoints

- Nature, frequency, and severity of adverse events, including serious adverse events, adverse events leading to discontinuation and possible corticosteroid-related adverse effects during the LTE from Week 61 to Week 113
- Average daily dose of CS from Week 61 to Week 113

- Time to initial flare/relapse from initial CDA to Week 109.

### 3. Overall Study Design and Plan

#### 3.1. Overall Design

This is a randomized, parallel-group, double-blind, placebo-controlled trial with 36 weeks of treatment during a Blinded Treatment Period followed by an Open-Label Extension Period of 24 weeks and Long Term Extension Period of 48 weeks and a Follow-up Period of 4 weeks.

Patients with moderate to severe pemphigus will be randomized in a 1:1 allocation ratio to receive either PRN1008 400 mg twice daily (bid) or placebo bid during a Blinded Treatment Period (Week 1 to Week 37). At screening, patients will be initiated on a daily dose of prednisone depending on disease severity. During the study, patients will undergo a moderately rapid CS taper regimen with the goal to reduce the CS dose to 5 mg/day by no later than Study Week 29, as appropriate.

From Week 37, all patients will receive active drug in the Open-Label Extension Period for 24 weeks. Patients who received placebo will thus receive active treatment with PRN1008 400 mg bid. Patients requiring treatment by rituximab or other immunosuppressants (other than CS) for relapse during this period, must be discontinued from the study. If a patient has a qualifying relapse during the Blinded Treatment Period and the second infusion from the rituximab course of treatment occurs during the Open-Label Extension period, the patient may continue in the trial. During the Open-Label Extension Period, further tapering of CS will be attempted to 0 mg for patients with CR.

After completing the Open-Label Extension Period, eligible patients (patients who are responding to PRN1008 treatment) may continue in the Long Term Extension Period of 48 weeks. Patients will continue to have a 4 week follow-up visit after the patient's last dose of PRN1008. During the Long Term Extension Period, patients will continue to receive open-label PRN1008 400 mg bid for 48 weeks.

#### 3.2. Sample Size and Power

The primary efficacy endpoint is the proportion of patients who are in CR from Week 29 to Week 37 with a CS dose of  $\leq 10$  mg/day.

### 3.3. Study Population

The study population is comprised of male and female patients with newly diagnosed or relapsing moderate to severe pemphigus (pemphigus vulgaris [PV] or pemphigus foliaceus [PF]).

### 3.4. Treatments Administered

Patients will be randomized to one of two treatments in a 1:1 allocation ratio:

- 400 mg of PRN1008
- matching placebo

Study investigational product (IP) taken twice daily by mouth starting on Day 1.

Required, initial doses of CS for the duration of Screening are  $\geq 0.2$  mg/kg/day of CS for patients with relapsing disease (diagnosed  $> 6$  months prior to Screening) and  $\geq 0.5$  mg/kg/day for patients with newly diagnosed disease (diagnosed  $\leq 6$  months prior to Screening). At Screening, patients will begin to take Sponsor-provided CS according to the minimum dose requirements, and as required to adequately treat the disease during the Screening period. CS doses may be adjusted per Investigator discretion during the Screening period, but the dose should not be reduced below the required minimum initial dose levels.

Thereafter, CS will be managed per the Corticosteroid and Rituximab Management protocol detailed in Appendix 1 of the protocol.

Rituximab treatment may also be administered during the Blinded Treatment Period after the Week 5 visit, unless contraindicated, after a second or subsequent, clinically significant “qualifying relapse” occurs. Full details on Rituximab treatment can be found in Appendix 1 of the protocol.

### 3.5. Method of Assigning Subjects to Treatment Groups

Patients who meet study criteria will be randomly assigned to placebo or PRN1008 in an approximately 1:1 allocation ratio. The randomization scheduled will be computer generated using a permuted block algorithm stratified by PV/PF disease type and by relapsing/newly diagnosed disease history (newly diagnosed defined as within 6 months of Screening).

The randomization schedule will be prepared by Premier Research before the start of the study. No one involved in the study performance will have access to the randomization schedule before the official unblinding of treatment assignment. No subject will be randomized into this study more than once.

### **3.6. Blinding and Unblinding**

All subjects, investigators, and study personnel involved in the conduct of the study, including data management, will be blinded to treatment assignment, and a specified unblinded statistician and programmer from [REDACTED], and as part of the integration of Principia Biopharma to Sanofi an independent programmer from Sanofi will have access to the randomization code. The unblinded study personnel will not participate in study procedures or data analysis prior to unblinding of the study data.

Study personnel will endeavor to safeguard the integrity of the study blind to minimize bias in the conduct of the study. Treatment unblinding is discouraged if knowledge of the treatment assignment will not materially change the planned management of a medical emergency. Unblinding will be permitted in a medical emergency that requires immediate knowledge of the subject's treatment assignment.

Unblinding should be discussed in advance with the medical monitor, if possible. For emergency unblinding, study personnel will use the interactive web response system (IWRS). In all cases that are not emergencies, the investigator should discuss the event with the medical monitor prior to unblinding the subject's treatment assignment.

If treatment assignment is unblinded for an individual subject, study personnel will be notified of that subject's treatment assignment without unblinding the treatment assignments for the remaining subjects in the study. Thus, the overall study blind will not be compromised.

### **3.7. Schedule of Events**

A detailed schedule of events for the blinded treatment period, open label portion, open label extension and Long Term Extension of the study are provided in the protocol.

## 4. Statistical Analysis and Reporting

### 4.1. Introduction

Data processing, tabulation of descriptive statistics, calculation of inferential statistics, and graphical representations will be performed primarily using SAS (release 9.4 or higher). If the use of other software is warranted, the final statistical methodology report will detail what software was used for what purposes.

Continuous (quantitative) variable summaries will include the number of subjects ( $n$ ) with non-missing values, mean, standard deviation (SD), median, minimum, and maximum.

Categorical (qualitative) variable summaries will include the frequency and percentage of subjects who are in the particular category or each possible value.

Analyses will be presented by the treatment group assigned at randomization for the Blinded Treatment Period of the study and by double-blind treatment group and overall for the Open Label Phase and Long-Term Extension Phase of the study, unless stated otherwise.

The minimum and maximum will be reported with the same degree of precision (i.e., the same number of decimal places) as the observed data. Measures of location (mean and median) will be reported to 1 degree of precision more than the observed data and measures of spread (SD) will be reported to 2 degrees of precision more than the observed data.

Percentages will be presented to 1 decimal place, unless otherwise specified.

Unless otherwise indicated, all statistical tests will be conducted at the 0.05 significance level using 2-tailed tests, and  $P$  values will be reported. Corresponding 95% confidence intervals (CIs) will be presented for statistical tests.

Statistical testing will be performed at the 0.05 level using two-tailed tests.

To control for the overall type I error rate, hierarchical testing based on a fixed sequence procedure will be used. If statistical significance is declared for the primary analysis, formal hypothesis testing will be done for the key secondary endpoints in sequence until a non-significant result is reached. All other  $p$  values from key secondary and other secondary endpoints, after a non-significant  $p$  value is reached, will be considered nominal.

### 4.2. Data Monitoring

A Data Safety Monitoring Board (DSMB) will be established to conduct reviews of subject safety. The DSMB reviews will occur approximately quarterly throughout the study unless the DSMB decides otherwise. Details of the operation of the DSMB are detailed in the DSMB charter. They can be modified as required. The unblinded analyses are performed by independent statisticians at Axio Research and the treatment codes are revealed to that party only. The unblinded DSMB listings will not be seen by anyone except the DSMB and the performing statistician.

No interim analyses are planned.

### 4.3. Timing of Analyses

Three sets of analyses are planned for this study.

1. After all patients have completed the week 37 (or early termination) study visit.
2. After all patients have completed the week 65 (or early termination) study visit.
3. At the end of the long term extension.

The first planned analysis will be performed after all enrolled subjects have completed the Week 37 (or Early Termination) study visit and will include subject activity occurring during the Blinded Treatment portion from Screening through Week 37. At this time, all data will be cleaned through Week 37 and the database will be locked prior to unblinding. A full set of analyses will be provided including disposition, demographics, protocol deviations, medical history, exposure and compliance through Week 37, all safety data summaries through Week 37, and all primary, secondary and exploratory efficacy endpoints through Week 37.

The second planned analysis will be performed after all subjects who have elected to participate in the Open-Label Extension Period have completed the Week 65 (or Early Termination) study visit. A full set of TLFs will be provided after the database has been cleaned and locked which will include all data collected during the open label portion of the study including disposition, demographics, protocol deviations, exposure and compliance between Week 37 and Week 61, all safety data summaries between Week 37 and Week 65.

In the above planned analyses, data collected after the target visit will also be presented either separately or combined with those prior to the target visit to have an overall assessment when appropriate (eg, exposure).

A third analysis will be conducted similarly following the end of the Long-term Extension period.

## 5. Analysis Populations

The following analysis populations are planned for this study:

- **Safety Population (SAF):** The Safety Population includes all patients who receive at least one dose of study medication. Safety analyses will be based on the safety population. Analyses of the SAF population will be presented based on actual treatment received. When a patient is exposed to both PRN1008 and placebo in the double blind period, the patient will be analyzed in the treatment group that the patient was exposed longer in the blinded treatment period.
- **Intent-to-Treat (ITT) Population:** The ITT Population includes all randomized patients.
- **Modified Intent-To-Treat (mITT) Population:** The mITT Population includes all patients who are randomized and receive at least one dose of study medication. Patients will be analyzed for efficacy according to the treatment group to which they were randomized.

**Pharmacokinetic and Pharmacodynamic Populations (PK and PD):** The PK and PD Populations include all subjects in the Safety Population who have sufficient data for PK and/or PD analysis.

Analyses of the mITT Population will be presented based on the assigned treatment including cases in which a subject is randomized incorrectly or is administered the incorrect IP.

## **6. General Issues for Statistical Analysis**

### **6.1. Statistical Definitions and Algorithms**

#### **6.1.1. Baseline Definitions**

Baseline values will be the last observation recorded prior to first dose of randomized treatment. Baseline value derivations will include evaluations specified to have been collected Pre-Dose on Day 1 as specified in study schedule. For patients from the ITT Population who are randomized but not treated, baseline will be based on their randomization date.

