### **Open-Label Extension Period (Weeks 37 to 61)**

From Week 37, all patients will receive active drug in the Open-Label Extension Period for 24 weeks per [Table 3](#). Patients who received placebo will thus receive active treatment with rilzabrutinib 400 mg bid. Patients requiring treatment by rituximab or other immunosuppressants (other than CS) for relapse/flare during this period, must be discontinued from the study. If a patient has a qualifying relapse/flare during the Blinded Treatment Period and the second infusion from the rituximab course of treatment occurs during the Open-Label Extension period, the patient may continue in the trial.

Patients that received rituximab during the Blinded Treatment Period and are continuing in the study, will complete TBNK testing (T and B and Natural Killer Lymphocyte Panel) at their Week 37 Visit.

From Week 37 (time of primary endpoint), further tapering to 0 mg CS should be attempted in patients with CR unless medically contraindicated. Patients who fail to respond to treatment or experience worsening of disease should have their CS dose increased per CS management guidelines (Appendix 1 [Section 12.1](#)) until CDA is obtained. If ECP is not achieved in a timely manner, it is encouraged that CS dose be further increased unless clinically contraindicated. The PI should consult with the Medical Monitor in such cases.

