#### **6.1.2. Study Day**

Day 1 is defined as the date of first dose of randomized treatment. Study day is calculated relative to the date of Day 1.

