## **9.2. Clinical Laboratory Evaluations**

Absolute values and changes from baseline will be summarized for clinical laboratory chemistry, hematology and coagulation results using descriptive statistics. The number of subjects with clinical laboratory values below, within, or above the normal range by time point will be tabulated for each clinical laboratory analyte. Shift tables for each clinical laboratory test will cross-tabulate the number of subjects with values below the laboratory reference range (low), values within the laboratory reference range (normal) or above the laboratory range (high) at baseline with the number of subjects with low, normal or high values at each post-baseline time point. Normal ranges and values outside the normal ranges will be identified by the central laboratory. A separate listing of out of normal range laboratory results will be provided.

A listing of all randomized subjects with pre-treatment and treatment-emergent laboratory values out of normal range will be presented.

Patients with positive urine pregnancy test results will be presented in by-subject listings.

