### **9.5. Electrocardiograms**

Descriptive summaries will be presented for ECG measures of PR interval, RR interval, QRS Duration interval, QTcF interval, and HR. These summaries will be presented by study visit.

Shift tables comparing baseline ECG investigator interpretation (normal; abnormal, not clinically significant; or abnormal, clinically significant) and unable to evaluate, to each study visit will be provided.

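### For placebo-first patients, open-label and long-term extension safety change and shift tables use a baseline taken 252 days before their first rilzabrutinib dose

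*SAP*

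**What the plan says.** SAP 6.1.1 states: "Baseline values will be the last observation recorded prior to first dose of randomized treatment". SAP 6.1.2 anchors study day to the same event: "Day 1 is defined as the date of first dose of randomized treatment". Neither the SAP nor the protocol defines another baseline for the open-label period, the LTE or the first active dose.

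The placebo arm changes treatment at Week 37. Protocol 4.1 says "Patients who received placebo will thus receive active treatment with rilzabrutinib 400 mg bid", and SAP 3.1 says the same.

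The single baseline feeds these safety outputs:

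- **Laboratory (SAP 9.2):** changes from baseline, and shift tables that cross-tabulate the range category "at baseline with the number of subjects with low, normal or high values at each post-baseline time point".
- **Vital signs (SAP 9.3):** changes from baseline.
- **ECG (SAP 9.5):** "Shift tables comparing baseline ECG investigator interpretation" with the interpretation at each study visit. Numeric ECG measures are only summarised by visit.

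SAP 9 has safety summarised separately for the blinded, open-label and LTE periods, by randomised arm and with an overall column. SAP 9.7 repeats laboratory and vital-sign summaries for the LTE. It does not name ECG, so LTE ECG shifts rest on the each-visit wording of 9.5.

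Adverse events are handled differently. Under SAP 6.1.8 and 9.1, an open-label treatment-emergent event must be new, or worse, relative to the patient's state in the blinded period.

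**The concern.** An open-label or LTE safety table is read as a picture of what happened on rilzabrutinib. For a placebo-first patient, the change shown starts before the first placebo tablet and runs through the whole blinded period. During that period "patients will undergo a moderately rapid CS taper regimen with the goal to reduce the CS dose to 5 mg/day", from a starting minimum of 0.2 or 0.5 mg/kg/day (Protocol Table 1). Protocol Appendix 6 lists body mass index, glucose tolerance and blood pressure among the domains of steroid toxicity, so glucose, weight and blood pressure can move without any rilzabrutinib.

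Two kinds of misplacement follow in the shift tables. A patient who was normal on Day 1 and became high on placebo is counted as a normal-to-high shift at an open-label visit. A patient who was high on Day 1, normal at Week 37 and high again on rilzabrutinib is counted as no shift. The overall column adds a further problem, because it pools these patients with rilzabrutinib-first patients, whose baseline does precede the drug.

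**Working it through.** The documents give no figure of their own to reproduce here. The check is a calculation on the SAP's nominal visit days, followed by a check that a pre-drug value exists.

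**Inputs**

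- SAP 3.1 describes a "double-blind, placebo-controlled trial with 36 weeks of treatment during a Blinded Treatment Period".
- Target days are from SAP 6.1.6, Tables 2 and 3: Week 37 = Day 253, Week 39 = 267, Week 49 = 337, Week 61 = 421, Week 85 = 589, Week 97 = 673, Week 109 = 757. Each equals (week − 1) × 7 + 1.
- First rilzabrutinib dose in the placebo arm: nominally Day 253.

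**Formulas**

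- Placebo days = 253 − 1 = 252, which is 36 weeks.
- Interval from baseline = target day − 1.
- On-drug days = target day − 253.
- Placebo share = 252 / interval.

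| Visit | Interval (days) | Placebo days | On-drug days | Placebo share |
|---|---|---|---|---|
| Week 39 | 266 | 252 | 14 | 94.7% |
| Week 49 | 336 | 252 | 84 | 75.0% |
| Week 61 | 420 | 252 | 168 | 60.0% |
| Week 85 | 588 | 252 | 336 | 42.9% |
| Week 97 | 672 | 252 | 420 | 37.5% |
| Week 109 | 756 | 252 | 504 | 33.3% |

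With a baseline at the last value before the first rilzabrutinib dose, the interval equals the on-drug days and the placebo share is 0% at every visit.

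**ECG.** Protocol 8.4.6 schedules ECGs at Screening and Weeks 37, 61 and 109, with none on Day 1. The ECG baseline is therefore normally the Screening tracing, and the gap to first rilzabrutinib exceeds 252 days.

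**Is a pre-drug value available?** Yes. Protocol Table 3 has weight, vital signs, hematology, chemistry and a 12-lead ECG at Week 37. Its footnote puts the first open-label dose on the evening of that visit, and the SAP's Week 37 analysis window closes before that dose.

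**Effect on a shift count (illustration only).** The documents give no shift rates, so all of these are assumptions: N = 55 crossover patients; a = proportion normal on Day 1 who became high on placebo and stayed high; h = proportion high on Day 1 but normal at Week 37; everyone else normal at both; 5% of those normal at Week 37 become high on drug.

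- Counted with the SAP baseline: 55 × [a + 0.05 × (1 − a − h)].
- New on-drug highs: 55 × 0.05 × (1 − a).
- a = h = 0: 2.75 counted, 2.75 on-drug.
- a = h = 0.05: 55 × 0.095 = 5.2 counted, 55 × 0.0475 = 2.6 on-drug.
- a = h = 0.10: 55 × 0.14 = 7.7 counted, 55 × 0.045 = 2.5 on-drug.
- a = 0, h = 0.10: 55 × 0.045 = 2.5 counted, 2.75 on-drug.

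The discrepancy can be nil, upward or slightly downward. Almost all of any excess comes from a.

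**The case against.** The strongest reply is that the information is largely recoverable from planned outputs. SAP 9.2 also tabulates absolute values and counts below, within and above range by time point, and lists out-of-range results. SAP 9 shows the placebo-first group in its own column. Week 37 is itself a tabulated visit, so patients already high when they start rilzabrutinib are visible as a group. Protocol 8.6.3.6 has clinically significant laboratory and ECG abnormalities recorded as adverse events, and open-label events are already judged against the blinded period. All of this stands. A reader might infer that the open-label tables cannot show what rilzabrutinib did in these patients, and the documents do not support that. What is missing is narrower: by-visit counts do not link a patient's Week 37 category to the same patient's later category, and hand-reading listings is a poor substitute for a shift table.

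A reader might also infer that Week 37 gives a uniquely clean starting point on a stable low steroid dose. That is not supported either. The 5 mg/day level is a goal, Protocol Appendix 1 provides for up-titration and for rituximab in the blinded period, and tapering to zero is to be attempted after Week 37 in patients in complete remission. Rilzabrutinib-first patients also have a pre-drug value.

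Nor should the illustrative counts be read as a predicted inflation. For glucose, falling steroid doses would more naturally move patients from high to normal than create lasting new highs, so even the direction is uncertain.

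Finally, SAP 9 plans no statistical tests on safety data. That stands, and it limits how much weight the point carries.

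**Conclusion.** The point holds as a weakness in method. One baseline serves every period, and in the placebo-first group it precedes rilzabrutinib by a nominal 252 days, or longer for ECG. The change and shift tables for that group therefore combine on-drug change with placebo-period and steroid-dose change, and the overall column mixes two kinds of baseline. The adverse-event rules in the same SAP already use a period-specific reference, so the two sets of tables for one period answer different questions.

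The affected group is the part of the placebo arm (about 60 patients, 1:1 allocation) that enters the open-label period. The placebo shares assume visits on target days and a first open-label dose on Day 253. The number of misplaced shifts cannot be stated from the documents. The consequence is confined to descriptive laboratory and vital-sign changes, laboratory shifts and ECG-interpretation shifts. No efficacy endpoint, error rate or power is affected, and numeric ECG change is not in question because none is planned.

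**What to change.** Add to SAP 6.1.1: *For change-from-baseline and shift summaries of safety data in the open-label and long-term extension periods, baseline is the last value before the patient's first rilzabrutinib dose. For patients randomised to placebo this is the Week 37 value before open-label dosing; for patients randomised to rilzabrutinib it is the existing baseline.* Refer to this rule in SAP 9.2, 9.3, 9.5 and 9.7. Keep the open-label and LTE tables on the randomised-dose baseline as a supplement, and leave the blinded-period tables unchanged.

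The cost is one derived variable and some extra tables, with no new data collection. Two limits should be noted with the tables. Changes from Week 37 have no concurrent control and can still reflect later steroid changes. The two arms' baselines will also sit at different points in the steroid taper, so the columns should not be compared as if randomised, and the overall column needs a footnote.
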